9.4.1 Reporting

Any unanticipated problem that occurs during the conduct of this study and that meets **at least** the first two criteria listed in section [9.3.19.2.1](#) must be reported to the UNC IRB by the Study Coordinator using the IRB's web-based reporting system (see section 11.5.3).

9.5 Data and Safety Monitoring Plan

The Principal Investigator will provide continuous monitoring of patient safety in this trial with periodic reporting to the Data and Safety Monitoring Committee (DSMC) as required.

Meetings/teleconferences will be held at a frequency dependent on study accrual, and in consultation with the study Biostatistician. At these meetings, the research team will discuss all issues relevant to study progress, including enrollment, safety, regulatory, data collection, and the team will produce summaries or minutes of these meetings. These summaries will be available for inspection when requested by any of the regulatory bodies charged with the safety of human subjects and the integrity of data including, but not limited to, the oversight (Office of Human Research Ethics (OHRE) Biomedical IRB, the Oncology Protocol Review Committee (PRC) or the North Carolina TraCS Institute Data and Safety Monitoring Board (DSMB).

10.0 STATISTICAL CONSIDERATIONS

10.1 Study Design

This is a pilot clinical trial of the PACT intervention in older adults with AML. The primary objective is to assess the feasibility (recruitment and retention) and acceptability of PACT intervention and examine change in pre and post measures of symptoms, function, and QOL comparing 10 control and 10 intervention patients with AML.

Qualitative research does not necessarily predict what might occur, but helps to understand in depth the characteristics of the situation and the meaning brought by participants and what is happening to them at that moment.

Interviews will be semi-structured, face to face with follow-up questions and probes to facilitate a deeper understanding of the patient, caregiver perceptions of the intervention. Interviews will take place on 4 oncology in patient's hospital room or private clinic room and will not last longer than one hour. An interview guide, developed in advance of data collection, will be used to provide a structure to the process (Appendix 13.1).

The interview prompts will focus on the overall perception of the PACT intervention. Each interview will be digitally audio-recorded. Brief field notes will be made before, during (in a non-discrete manner) and after the interviews to make note of points thought to be relevant at the time.

Pseudonyms will be used to protect the identity of the participants. The pseudonym will be linked to demographic and clinical information in a master log. The master log of study participants' names and study codes will be kept in a secure file cabinet in the investigator's locked office.

10.2 Sample Size and Accrual

Sample size for this study is mainly determined by time and resource (budget) constraints. We will allocate 26 patients to the two groups (12 per group). We assume 20% of values will be missing or otherwise unusable, yielding complete data for 10 patients per group for analyses. As stated

above, estimation rather than statistical inference is our focus, and so it is not this project's goal to have adequate statistical power. We can focus instead on precision, and for the primary outcome of QOL (standardized), the half-width of a two-sided 95% confidence interval would be .9SD, assuming 10 patients per randomized group. We obtained this result using nQuery Advisor v7.0 software.

We claim such a study as feasible if and only if both (a) recruitment rate (p) is high enough and (b) retention rate (q) is sufficiently high, i.e., if both p and q are large enough. More specifically, this is to test the following hypothesis:

$$H_0: p \leq 50\% \text{ or } q \leq 50\% \text{ vs } H_1: p \geq 80\% \text{ and } q \geq 70\%.$$

Denote N as the number of eligible patients we try to recruit, and Y as the number of patients who are recruited, X as the number of patients (among the Y who are enrolled) who complete the PACT intervention. The target value of Y is 20, and we assume (1) N follows a negative binomial distribution, $NB(20, p)$, (2) X , conditional on ($Y = 20$), follows a binomial distribution $B(20, q)$. We further assume that N and X are independent. We list cut-offs and associated type I error and power under different N and X values for rejecting the hypothesis of $p \leq 50\%$ and the hypothesis of $q \leq 50\%$.

Recruitment (N: total number of patients being approached)

Y	Rejection Area	Type I error ($p \leq 50\%$)	Power ($p \geq 0.80$)
20	$N \leq 20+12$	0.108	0.994
20	$N \leq 20+13$	0.148	0.997
20	$N \leq 20+14$	0.196	0.999
20	$N \leq 20+15$	0.250	0.999

Retention (X: total number of patients who complete the intervention)

Y	Rejection Area	Type I error ($q \leq 50\%$)	Power ($q \geq 0.70$)
20	$X > 8$	0.748	0.995
20	$X > 9$	0.588	0.983
20	$X > 10$	0.412	0.952
20	$X > 11$	0.252	0.887

Under the independence assumption, the overall Type I error rate is the product of two individual type I errors, and the overall power is the product of power of two individual powers. We will reject the hypothesis of $p \leq 50\%$ if $N \leq 34$, and reject the hypothesis of $q \leq 50\%$ if $X > 11$. The resulted overall type I error is 4.9%, while the overall power is 88.6%.

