1.0 BACKGROUND AND RATIONALE

1.1 Study Synopsis

This single institution feasibility and acceptability of study methods are to examine change in pre and post measures of symptoms, function, and QOL comparing 10 control and 10 intervention patients with acute myeloid leukemia (AML). AML is the most common type of acute leukemia. This study is designed to examine a novel palliative and collaborative care intervention in which registered nurses (RNs), occupational therapists (OTs) and physical therapists (PTs) address the physical activity needs of older adults (≥ 60 years) with AML during cycles 1 and 2 (approximately 60 days) of a Palliative and Collaborative Care in Tervention (PACT) (intervention arm only). The eligible population will include patients at the North Carolina Cancer Hospital (NCCH) with a diagnosis of AML, age ≥ 60 years, and receive hypomethylating agents (HMA) or low-dose cytarabine + Venetoclax.

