2.0 STUDY PURPOSE AND DESIGN

This is a single institution, feasibility trial of 20 (10 control and 10 intervention) patients with the primary objective of assessing feasibility, acceptability, and change in pre and post measures of symptoms, function, and QOL by administering the PACT intervention.

Study subjects will be identified by the Study Coordinator through pre-screening through the electronic health record after being referred by the oncologists and pharmacists. Eligible patients will be approached by the Study Coordinator to confirm eligibility, which includes requesting permission of the patient's attending physician. Seven days prior to and within three days after initiation 1st cycle HMA or low-dose cytarabine + VENE, written informed consent will be obtained (A total of 10 days of recruitment period and baseline assessment).

First, ten participants in the control group will receive usual care. After the control patients have completed the study, then 10 intervention participants will receive the PACT intervention, a novel symptom management intervention, which aims to build patient skills to manage AML treatment-related, and chronic illness symptoms. Because patients receive chemotherapy during the first 7 days of hospitalization or clinic visit, the intervention will start at day 1 or day 2 of chemotherapy. During hospitalization, the PACT RN will assess AML symptoms daily (using PRO-CTCAE), and PACT OT and PT will assess function at baseline (day 1 or 2), days 3 or 4, and days 6 or 7. This study uses UNC hired staff of RNs, OTs, and PTs to deliver the intervention.

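### Section 10.2 gives three enrolment totals (26, 12 per group = 24, and 20); at the 20 enrolled stated elsewhere, the plan's own 20% loss leaves 8 complete patients per group, not the 10 behind the .9 SD half-width.

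*Combined protocol and SAP*

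**What the plan says.** Section 10.2 opens with the allocation: "We will allocate 26 patients to the two groups (12 per group). We assume 20% of values will be missing or otherwise unusable". The section describes the result of that loss as "yielding complete data for 10 patients per group for analyses". It says that precision, not power, is the focus, and gives the precision as follows: "the half-width of a two-sided 95% confidence interval would be .9SD, assuming 10 patients per randomized group".

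The feasibility test later in section 10.2 uses a different total. Y is defined as the number of patients recruited, and "The target value of Y is 20". The recruitment and retention tables are both built on that value.

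The rest of the document plans 20. Section 2.0 says "This is a single institution, feasibility trial of 20 (10 control and 10 intervention) patients" and makes the groups sequential: "After the control patients have completed the study, then 10 intervention participants will receive the PACT intervention". Sections 1.1, 3.1, 5.1 and 10.1 also give 10 control and 10 intervention patients. Section 5.1 describes the 20 as patients to be enrolled over two years, and adds that the first 10 go to the control group.

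**The concern.** Twice 12 is 24, so the allocation sentence does not agree with itself. Neither 24 nor 26 agrees with the 20 used later in section 10.2 and in the design sections. No section explains the difference.

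The inconsistency matters because two results in section 10.2 rest on different totals. The 10 complete patients per group, and so the .9 SD half-width, need more than 20 enrolled if 20% is lost. The feasibility cut-offs are worked out at exactly 20. The plan offers precision in place of power as the rationale for its size, so the half-width is a figure it relies on. Because the control group is filled first, the total also decides how many controls are taken before the intervention group opens.

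**Working it through.** **Inputs.** From section 10.2: 26 allocated, 12 per group, 20% loss, 10 complete per group, half-width .9 SD, Y = 20, and cut-offs N ≤ 34 and X > 11. From sections 2.0 and 5.1: 20 enrolled, 10 per group.

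**1. Reproduce the allocation.** Enrolment needed for 10 complete at 20% loss is n/(1 − d) = 10/0.8 = 12.5, so 13 per group and 26 in total. The 26 reproduces. The other common form, n × (1 + d) = 10 × 1.2 = 12, gives 12 per group and 24 in total, and may be where the 12 comes from. Checked forwards, it falls short: 12 × 0.8 = 9.6.

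**2. Reproduce the half-width.** For a difference between two group means in SD units, the half-width is crit × sqrt(2/n). At n = 10:
- z: 1.96 × sqrt(0.2) = 0.877
- t, 18 df: 0.940

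Both round to the stated .9 SD, so that figure is right for 10 complete per group.

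**3. Apply the plan's loss to each total.**

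| Enrolled | Complete per group after 20% loss |
|---|---|
| 26 | 26 × 0.8 / 2 = 10.4 |
| 24 | 24 × 0.8 / 2 = 9.6 |
| 20 | 20 × 0.8 / 2 = 8 |

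**4. Half-width at 8 per group.**
- z: 1.96 × sqrt(2/8) = 0.980; ratio to n = 10: 0.980/0.877 = 1.118
- t, 14 df: 1.072; ratio to n = 10: 1.072/0.940 = 1.141

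**5. Check which total the feasibility tables use.** N is negative binomial and X binomial, as section 10.2 assumes. The row for Y = 20 reproduces the plan's figures, with products 0.196 × 0.252 = 4.9% and 0.999 × 0.887 = 88.6%. The row for Y = 26 applies the same cut-offs to 26 recruits.

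| Y | N ≤ 34: type I error / power | X > 11: type I error / power |
|---|---|---|
| 20 | 0.196 / 0.999 | 0.252 / 0.887 |
| 26 | 0.0015 / 0.773 | 0.721 / 0.997 |

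The stated operating characteristics therefore belong to Y = 20 only. This checks the tables' arithmetic and nothing else about the feasibility rule.

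**The case against.** **20 as completers.** The best defence is that 20 means evaluable patients and 24 to 26 means enrolled patients. The comparison wording in sections 1.1 and 10.1 would fit that. Section 5.1 does not, because it speaks of enrolling 20, and section 10.2 defines Y as patients recruited. The defence fails.

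**20% of values.** The 20% is worded as a share of values, not patients. But section 10.2 itself turns it into complete patients per group, so step 3 follows the plan's own use.

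**Analysis method.** The planned ANCOVA could narrow the interval, and section 10.3 says multiple imputation will be considered if missing data are extensive. Both points are fair. However, the gain from ANCOVA depends on a baseline correlation that the documents do not give. Imputation that kept all 10 enrolled per group would give 0.88 to 0.94 SD unadjusted at best. Neither is the basis on which the .9 SD is stated, which is complete data for 10 per group.

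**Little depends on it.** Section 10.2 says the size is set by time and budget and disclaims a power goal. Section 10.3 plans no significance testing. Moving from about 0.9 to about 1.0 SD changes no stated decision. This stands, and it limits the weight of the point.

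**Readings that go too far.** A reader might infer that 26 is a miscalculation. It is not: it is 2 × 13, and the 12 per group is the misfit. A reader might also infer that nobody could tell when to stop accrual. Sections 2.0 and 5.1 give one consistent instruction (10 controls, then 10 intervention patients), and the allocation sentence is the outlier.

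**Conclusion.** The inconsistency is real. Section 10.2 holds three incompatible totals, and at the 20 enrolled stated elsewhere the 10 complete per group and the .9 SD half-width do not follow from the plan's own loss assumption. The consistent figures are 8 per group and about 0.98 to 1.07 SD. This rests on the 20% loss falling equally on both groups and on an unadjusted comparison of complete cases.

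The consequence is a descriptive interval 12% to 14% wider than stated, and a mismatch between the feasibility tables and the allocation sentence. A reader might conclude that the stated feasibility error rates are therefore wrong. The documents do not support that on this point: the tables match the 20 enrolled in the design sections, and come into question here only if 26 is the real target. The correction is worth making, but it does not undermine the design.

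**What to change.** State one enrolment total and one per-group number throughout.

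- **If the total is 20**, as the operational sections say: in the allocation sentence of section 10.2, change the total to 20 and the per-group number to 10. Restate the expected complete data as 8 per group, with an unadjusted 95% half-width of about 0.98 SD (z) to 1.07 SD (t). The feasibility tables keep their total of 20. The cost is rewording the allocation and precision sentences and accepting a slightly less favourable precision figure.
- **If 26 is already the intended accrual**: write 13 per group in section 10.2. Align sections 1.1, 2.0, 3.1, 5.1 and 10.1, including the statement in section 5.1 on the first 10 patients. Reconcile the feasibility tables with that total, since their type I error and power hold only at Y = 20. The cost is a sentence or two in each of those sections and a review of the tables. No patients are added beyond those already intended.

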3.0 STUDY OBJECTIVES/ENDPOINTS

3.1 Primary Objective

Determine feasibility and acceptability of study methods and examine changes in pre- and post-treatment measures of function, patients' self-report of symptoms and QOL, and patients and caregivers' post self-report of readiness for discharge. We will include 10 control and 10 intervention patients.

Feasibility: We plan enrollment of 60% of those approached; achieve 75% retention rate, 75% of intended data collection; and no intervention-related adverse events. The PACT intervention team will have a reduced workload; we will record effort required to deliver the PACT intervention. These feasibility data will inform if, or to what extent, workload is affected to plan future studies and implementation. The team will receive 32 hours of training in palliative care and adaptive leadership approaches. Adherence will be monitored by electronic tracking from OT and PT notes and by self-report.

Acceptability: Assessed by interviews and surveys with patients and their caregivers about their experiences.

Changes in pre-and-post QOL, symptoms, and function: Compare changes between control and intervention.

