3.4 Primary Endpoint

3.4.1 Feasibility will be defined as: % approached, retention rate (% of consented patients who completed the intervention); % intended data collection, safety (# of adverse events).

3.4.2 Adherence will be monitored by electronic tracking from OT and PT notes and by self-report during the intervention.

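### Section 10.2 needs at least 12 PACT completers to declare feasibility, but only 10 patients receive PACT, so the rule cannot be met as defined

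*Combined protocol and SAP*

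**What the plan says.** **Definition of retention.** Section 10.2 describes X as "X as the number of patients (among the Y who are enrolled) who complete the PACT intervention", and the retention table repeats this: "Retention (X: total number of patients who complete the intervention". The primary endpoint in Section 3.4 agrees: "retention rate (% of consented patients who completed the intervention".

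**Model and rule.** Given Y = 20 enrolled, Section 10.2 takes X as B(20, q). It rejects q ≤ 50% when X > 11 and rejects p ≤ 50% when N ≤ 34. The study counts as feasible only when both conditions hold. The stated joint figures are 4.9% type I error and 88.6% power.

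**Who receives PACT.** Section 1.1 restricts it: "Palliative and Collaborative Care in Tervention (PACT) (intervention arm only". Section 2.0 sets the order of enrolment: "First, ten participants in the control group will receive usual care", and "then 10 intervention participants will receive the PACT intervention". Sections 3.1 and 10.1 also give 10 and 10.

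**Text that points elsewhere.** Section 3.1 aims to "Determine feasibility and acceptability of study methods" and to "achieve 75% retention rate, 75% of intended data collection". Section 10.3 computes retention among those enrolled as one minus the proportion lost to attrition from the study. Section 10.2 also mentions allocating 26 patients, with 12 in each group.

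**The concern.** The definition of X, its binomial model and the allocation cannot all be right. A usual-care patient cannot complete PACT, so controls cannot contribute to X as defined, yet the model gives each of the 20 enrolled patients a chance q of being counted.

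The rule decides the primary endpoint. An analyst who follows Sections 3.4 and 10.2 would count at most 10 and declare the study infeasible, whatever happened. An analyst who follows Section 10.3 could declare it feasible from the same data. The two readings also answer different questions: whether patients complete PACT, and whether patients in both groups stay in the study.

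**Working it through.** **Inputs.** From Section 10.2: Y = 20; rule N ≤ 34 and X > 11; null p ≤ 50% or q ≤ 50%; design values p = 80%, q = 70%. From Section 2.0: 10 patients receive PACT and 10 receive usual care.

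**1. Reproduce the plan's figures.** N ≤ 34 means that at least 20 of the first 34 patients approached enrol. X > 11 means X ≥ 12.

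| Component | Formula | Null value (50%) | Design value |
|---|---|---|---|
| Recruitment | P(Bin(34, p) ≥ 20) | 0.1958 | 0.9988 (p = 80%) |
| Retention | P(Bin(20, q) ≥ 12) | 0.2517 | 0.8867 (q = 70%) |
| Product | | 0.0493 | 0.8856 |

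These match the stated 0.196 and 0.999, 0.252 and 0.887, and 4.9% and 88.6%. The arithmetic is right for 20 possible completers.

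**2. Apply the written definition.** Only the 10 PACT patients can be counted, so X ≤ 10 < 12. Hence P(X > 11) = 0 at every q, including q = 100%, and joint power is 0 × 0.9988 = 0, against 88.6% stated.

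**3. Test the other allocation.** The figures 26 and 12 per group conflict (2 × 12 = 24), and neither fits Y = 20. Taking each at face value:

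| PACT patients | Needed | P at q = 70% | P at q = 90% |
|---|---|---|---|
| 12 (24 enrolled) | 12 of 12 | 0.7^12 = 0.0138 | 0.9^12 = 0.2824 |
| 13 (26 enrolled) | 12 or 13 of 13 | 13 × 0.7^12 × 0.3 + 0.7^13 = 0.0637 | 0.6213 |

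The rule becomes attainable but very unlikely to pass at the design value.

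**4. Check the endpoint in Section 3.4.** Completers of PACT divided by all consented patients is at most 10/20 = 50%. It is also 50% at most with 12/24 or 13/26. That ceiling is below the 75% target in Section 3.1 and equals the upper edge of the null q ≤ 50%, so a rate of 70% is unreachable.

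**5. Read X as study retention in both groups.** All 20 can count, and the tabulated 0.252 and 0.887 stand. They then describe study retention, not completion of PACT.

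**6. Check the joint error on that reading.** The null is a union: either rate may be low. The product 0.1958 × 0.2517 = 0.0493 applies only at p = q = 50%. At p = 80%, q = 50%, still inside the null, the rule passes with probability 0.9988 × 0.2517 = 0.2514. At p = 50%, q = 70% it passes with probability 0.1958 × 0.8867 = 0.1736. The maximum is the larger component, max(0.2517, 0.1958) = 0.2517.

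**7. Rules that would test PACT completion, X ~ B(10, q), with N ≤ 34.**

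| Cutoff | Error at q = 50% | Power at q = 70% | Joint power (× 0.9988) | Maximum joint error |
|---|---|---|---|---|
| X ≥ 6 | 0.3770 | 0.8497 | 0.8487 | 0.3770 |
| X ≥ 7 | 0.1719 | 0.6496 | 0.6488 | 0.1958 |
| X ≥ 8 | 0.0547 | 0.3828 | 0.3823 | 0.1958 |

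**The case against.** The strongest reply is that the plan already contains a workable definition. Section 10.3 bases retention on attrition among all enrolled patients, which fits Y = 20, B(20, q), X > 11 and the printed error and power. On that view X is misworded around a sound calculation. This is the likelier intent. It does not settle the matter, because the completion wording appears three times: in the primary endpoint, in the definition of X and in the table heading.

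A second reply is that 12 or 13 PACT patients would make the rule attainable. That is true, but the allocation sentence contradicts itself and Y = 20, and step 3 shows how little it helps at q = 70%.

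A third reply is that this is a budget-limited pilot focused on estimation, with retention reported alongside a 95% confidence interval. That limits the harm, and no safety or stopping rule depends on X. The plan nevertheless makes feasibility conditional on X and attaches error and power to that decision.

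The type I error point is separate in origin: it would hold however X were defined. It belongs here because the same sentences must be rewritten.

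**Conclusion.** The concern holds. With 10 PACT patients and X as defined, the retention condition has probability 0, against a stated 88.7%, and the joint rule has power 0, against 88.6%. This conclusion needs no assumption about completion rates. It rests only on the 10 and 10 allocation given in Sections 1.1, 2.0, 3.1 and 10.1, and on controls not receiving PACT. If study retention among all 20 was meant, the component figures are correct and the fault lies in the definition. Either way, the definition has to be corrected before the primary endpoint is analysed.

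**What to change.** **Recommended change.** In Sections 3.4 and 10.2, including the table heading, define X as patients retained in the study among all 20 enrolled in both groups, matching Section 10.3. Keep X > 11, with component error 0.252, component power 0.887 and joint power 88.6%. State that the rule tests study retention. Report completion in the PACT arm separately with its exact 95% confidence interval; for example, 7 of 10 gives 35% to 93%. Reconcile the figures 26, 12 per group and Y = 20.

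**Alternative, if PACT completion is the question.** Define X among the 10 PACT patients, choose one cutoff from step 7 in advance, and report control retention separately. This is a trade-off and is not needed to remove the contradiction.

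**Under either choice**, replace the 4.9% overall type I error with the maximum under the stated null: about 25% for the recommended rule, or about 38%, 20% and 20% for the three alternative cutoffs.

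**Cost.** Wording only for the recommended change, with no extra patients or data. The stated error rises from 4.9% to about 25%, but that comes from correcting the product claim. Redefining X changes no error rate in the table. The alternative also needs a recomputed retention table and accepts joint power between 84.9% and 38.2%.

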5.0 STUDY PLAN

5.1 Patient Identification and Consent /Study Schema

Potentially eligible patients will be identified through pre-screening the Electronic Health Record after referring by oncologists or pharmacists. Eligible patients will be approached to confirm eligibility (which includes requesting permission of the patient's attending physician). The study coordinator will provide information about the study and invite participation. Seven days prior to and within three days after initiation 1st cycle HMA or low-dose cytarabine + VENE, written informed consent will be obtained from those eligible and interested in participating. If applicable, reasons for declining participation in the study will be recorded.

Study Schema

Recruitment of Patients

Approximately 100-150 patients with acute leukemia are admitted to UNC for treatment annually. We aim to enroll 20 patients (10 control and 10 intervention) with AML over 2 years. Given that recruitment to a pilot cluster randomized feasibility and acceptability trial may be lower than for an observational study, we project achieving our target sample within this timeframe.

Potentially eligible patients (diagnosis with AML) will be approached for enrollment by the study coordinator. Oncologists and nurse navigators will be provided a recruitment flier for the

study containing the purpose, a brief explanation of study protocols, and research team members' information. If the patient expresses interest in participating, the physician or pharmacist will relay this information to a research team member, who will provide more information about criteria for participation and a brief explanation of the study. Eligible patients will have up to 7 days before and within 3 days after initiation of chemotherapy to enroll in the study, and, if applicable, reasons for declining participation in the study will be recorded.

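### The feasibility cut-offs N≤34 and X>11 are calibrated only for exactly 20 enrolled, while the same section allocates 24 or 26 patients and gives no rule for any other number

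*Combined protocol and SAP*

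**What the plan says.** Section 10.2 calls the study feasible only when the recruitment rate p and the retention rate q are both shown to be high enough. The null is p≤50% or q≤50%; the alternative is p≥80% and q≥70%.

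- Recruitment: "The target value of Y is 20, and we assume (1) N follows a negative binomial distribution" with parameters 20 and p. N is the number of patients approached, and p≤50% is rejected if N≤34.
- Retention: given 20 enrolled, X is binomial(20, q), and q≤50% is rejected if X>11. X is defined as "X as the number of patients (among the Y who are enrolled) who complete the PACT intervention".
- Every row of both cut-off tables has Y = 20. The stated overall type I error is 4.9% and the stated power 88.6%.

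Other statements bear on whether Y will be 20:

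- Section 10.2 opens with "Sample size for this study is mainly determined by time and resource (budget) constraints", then allocates 26 patients, given as 12 per group.
- Section 5.1: "We aim to enroll 20 patients (10 control and 10 intervention) with AML over 2 years". It projects that this will be achieved.
- Section 2.0: "After the control patients have completed the study, then 10 intervention participants will receive the PACT intervention".

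Section 10.3 reports the enrolment and retention proportions with 95% confidence intervals.

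**The concern.** Both cut-offs are raw counts, so their meaning depends on Y. Twelve completers is 60% of 20, but 80% of 15 and only 50% of 24, and 50% is the null rate itself. If enrolment ends anywhere but 20, the printed rule becomes a different test with different error rates, and the plan does not say what replaces it.

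The plan gives two reasons to expect that Y may not be 20. Its own allocation figure is larger, and its size is tied to time and money. The sequential arms add a third. PACT recruitment waits for the controls to finish (last scheduled assessment at about day 90 in Table 5; about 6 months in section 5.4). Patients cannot be held over in that gap, because consent closes three days after chemotherapy starts.

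At stake is the trial's main quantitative conclusion. With Y above 20, the retention half can be passed at a completion rate no better than the null. With Y below 20, it can be failed at a rate the plan calls good.

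**Working it through.** **Inputs.** From section 10.2: null rates 0.5 and 0.5, alternatives 0.8 and 0.7, Y = 20, cut-offs N≤34 and X≥12, and the competing totals 26 and 2×12 = 24. Write T(n, k, π) = P(Bin(n, π) ≥ k). By negative binomial–binomial duality, the chance that the Yth enrolment comes within n approached is T(n, Y, p).

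**1. The plan's own figures.**
- Recruitment: T(34, 20, 0.5) = 0.196; T(34, 20, 0.8) = 0.999.
- Retention: T(20, 12, 0.5) = 0.252; T(20, 12, 0.7) = 0.887.
- Products: 0.1958 × 0.2517 = 0.0493 and 0.9988 × 0.8867 = 0.8856.

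All agree with section 10.2 to rounding.

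**2. X>11 left fixed while Y changes.**

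| Y | 12/Y | Type I error T(Y, 12, 0.5) | Power T(Y, 12, 0.7) |
|---|---|---|---|
| 15 | 80% | 0.018 | 0.297 |
| 16 | 75% | 0.038 | 0.450 |
| 18 | 67% | 0.119 | 0.722 |
| 20 | 60% | 0.252 | 0.887 |
| 24 | 50% | 0.581 | 0.988 |
| 26 | 46% | 0.721 | 0.997 |

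**3. N≤34 when fewer than 20 enrol.** Taken literally, with N the total approached, 15 enrolled of 34 (15/34 = 44%) meets N≤34 and rejects p≤50%. Yet T(34, 15, 0.5) = 0.80, so the data give no evidence against p≤50%. If N is instead read as the number approached to reach the 20th enrolment, the type I error cannot exceed 0.196. Stopping after 30 or 28 approached then gives 0.049 or 0.018, with power at p = 0.8 of 0.974 or 0.910.

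**4. The definition of X.** X counts completers of PACT, and with 20 enrolled only 10 receive PACT. As defined, X is at most 10 and X>11 cannot be reached. The retention figures above therefore assume that X means completion by all enrolled patients, as B(20, q) implies.

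**5. Can the chance of a shortfall be derived?** Section 5.1 gives 100–150 acute leukemia admissions a year but not the share who are eligible. Assume Poisson enrolment, 125 admissions a year, p = 0.6 and 24 months less a 6-month gap. The mean is then 125 × share × 0.6 × 18/12, where share is the fraction of admissions eligible and approached:
- share 10%: mean 11.25, P(Y≥20) = 0.01
- share 15%: mean 16.9, P(Y≥20) = 0.25
- share 20%: mean 22.5, P(Y≥20) = 0.73
- share 30%: mean 33.75, P(Y≥20) = 0.996

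The unknown share decides the answer.

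**The case against.** The strongest reply is that the negative binomial model, with Y = 20 in every table row, already defines N as the number approached to enrol 20. A trial that stops short has then simply not met the recruitment criterion. Both halves are required, so no feasibility claim follows, and the loss of retention power at Y = 15 or 16 changes no decision. On that reading the rule is conservative below 20. This is a fair reading and it largely disposes of the literal 15-of-34 example, but the plan does not state it. It also does nothing for Y = 24 or 26, where the retention half errs towards a false claim.

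A reader might infer that a shortfall is likely. The documents do not support that. Section 5.1 projects success, the eligible share is missing, and step 5 runs from near-certain failure to near-certain success. Applying the average pace of 20 in 24 months and then removing the gap between arms would also load the answer, because the gap falls inside the same 24 months.

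A reader might also take two years as a hard cap, or want 20 enrolled within 24 months made a condition of feasibility. Section 5.1 states an aim, and sections 3.1, 3.4 and 10.2 set no calendar criterion. Such a condition would also make any cut-off for Y<20 pointless.

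The confidence intervals in section 10.3 can be computed for any Y. That helps interpretation but does not replace the decision rule in 10.2.

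**Conclusion.** The point holds as a gap in the decision rule. The component error rates in 10.2 are correct at exactly 20 enrolled and at no other number, and the section's own allocation contradicts that number. The best-documented consequence needs no accrual assumption: at the plan's 24 or 26 patients, X>11 has a retention type I error of 0.58 or 0.72 instead of 0.252. Below 20, retention power at q = 0.7 falls from 88.7% to 72%, 45% and 30% at Y = 18, 16 and 15. The recruitment misfire is narrower: it needs N read literally, and both Y<20 and N≤34 at closure.

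These figures assume binomial counts and all enrolled patients as the denominator of X. They concern the component tests only. The overall 4.9% is the error at p = q = 0.5; because the null is a union, it is higher elsewhere (0.251 at p = 0.8, q = 0.5). That is a separate matter.

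**What to change.** In section 10.2:

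1. Reconcile 20 with 24 and 26, and state the planned enrolment once.
2. Put X on the same denominator as Y. Either X is completion of the study by all enrolled patients, or X is PACT completion with the PACT arm as denominator and a recomputed cut-off.
3. Define both tests on the counts observed when accrual closes. Reject p≤50% if P(Bin(N, 0.5) ≥ Y) ≤ 0.196, and reject q≤50% if P(Bin(Y, 0.5) ≥ X) ≤ 0.252. These are the plan's current per-test levels.

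With all enrolled as denominator, this gives:

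| Y | Recruitment | Retention | Retention type I error | Retention power at q = 0.7 |
|---|---|---|---|---|
| 16 | N≤26 | X≥10 | 0.227 | 0.825 |
| 18 | N≤30 | X≥11 | 0.240 | 0.859 |
| 20 | N≤34 | X≥12 | 0.252 | 0.887 |
| 24 | N≤41 | X≥15 | 0.154 | 0.847 |
| 26 | N≤45 | X≥16 | 0.163 | 0.875 |

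The row for 20 is the existing rule. Calendar time need not enter the claim; enrolments per month of open recruitment can be reported descriptively.

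The cost is a few sentences and this table, with no extra patients or data. Because counts are discrete, retention power at other Y is somewhat below 88.7%: 82% at Y = 16, and 72% at Y = 15 (T(15, 10, 0.7)). Choosing the PACT arm as denominator costs more. With 10 PACT patients the same level gives X≥7, type I error T(10, 7, 0.5) = 0.172 and power T(10, 7, 0.7) = 0.650.
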